## 2 INTRODUCTION

Alzheimer's disease (AD) continues to cause a tremendous impact on the lives of millions of patients and their caregivers and puts a huge burden on healthcare systems worldwide. In the absence of effective disease modifying treatments, AD continues to represent a major area of unmet medical need. Cortexyme is developing a novel small molecule, COR388 HCl, for the treatment of AD. The development of this compound represents a new paradigm for disease modification in AD that is based on a large body of emerging scientific data from both Cortexyme and independent researchers, as detailed in the Investigator's Brochure (IB) and summarized in the sections below.

Cortexyme has discovered evidence of *Porphyromonas gingivalis* (*P. gingivalis* [*Pg*]) in the brains of a large proportion of Alzheimer's patients compared to controls. *P. gingivalis* is a Gram-negative asaccharolytic pathogen and a keystone bacterium in the development of periodontal disease. Gingipains are cysteine proteases produced by *Pg* that are critical for the survival of the bacteria, host cell toxicity, and immune evasion. *P. gingivalis* infection has been identified as a risk factor for a number of chronic inflammatory disease states including AD, atherosclerosis, and type 2 diabetes. *P. gingivalis* has been isolated from a variety of human tissues indicating systemic translocation beyond the oral cavity. A growing body of epidemiological evidence and prospective observational studies link periodontal disease, the most prevalent age-related chronic infection in humans, to diagnosis and rapid decline of AD. Cortexyme conducted a series of experiments to evaluate the presence of *Pg* and gingipains in the brains of AD patients and control groups, explore the role of *Pg* in the pathogenesis of AD, and evaluate gingipains as a therapeutic target. Based on the data summarized in the IB, Cortexyme believes this compound will slow or prevent further neurodegeneration, cognitive decline, and accumulation of pathology in AD patients.

COR388 HCl is a proprietary small molecule that is a potent and selective irreversible inhibitor of the bacterial protease lysine gingipain (Kgp) that was selected as a lead compound to progress toward human clinical trials based on its selectivity, pharmacokinetics (PK), efficacy, and safety profiles.

A comprehensive program was conducted to assess the PK, safety, and toxicity of COR388 HCl in 2 animal species and humans. COR388 HCl has a favorable PK profile in animals, and is readily bioavailable after oral administration, resulting in sufficient plasma and central nervous system (CNS) exposures for clinical efficacy. COR388 is a chiral molecule whose epimer COR490 is produced in vivo and has a similar potency, efficacy and PK profile. COR388 has a moderate level of plasma protein binding in animal species tested and human subjects. COR388 is cleared rapidly, with a terminal half-life ranging from 2-3.5 hours in different animal species to 4.5-5.0 hours at steady state in humans.

No evidence of genotoxicity was found on either a battery of in vitro studies in bacteria and mammalian cells or in an in vivo micronucleus study. General toxicology studies in mice and dogs showed no change in serum chemistry,

hematology, and urinalysis laboratory parameters. Treatment with large doses of COR388 was associated with transient cardiovascular effects in dogs. Histopathology evaluation with light and fluorescent microscopy, as well as electron microscopy, revealed minimal increase in the size and number of intracytoplasmic lysosomes in the brain in mice and dogs and the kidney in dogs. There was no evidence of cellular injury. These were considered an adaptive response by the neurons and renal tubular cells aiming at clearing excess COR388 and metabolites, that may not be expected to occur with the lower exposure levels planned in human trials. These findings were considered non-adverse in dogs at all doses, and in mice treated with doses  $\leq 100$  mg/kg/day. After a 28-day recovery period, a complete reversal of the findings was found in the kidneys in dogs and the stratum radiatum in mice, with partial recovery in other parts of the mouse brain.

Safety pharmacology studies revealed transient, and reversible effects on the cardiovascular and CNS systems. The no observed adverse effect levels (NOAELs) associated with these effects provide large safety margins over the doses used in this trial.

Cortexyme has completed two Phase 1 safety and PK studies. The Phase 1 program included a single ascending dose study in normal healthy volunteers, and a multiple ascending dose study in older healthy volunteers and AD subjects with clinical evidence of periodontitis.

Results from the single ascending dose study showed that COR388 HCl was absorbed rapidly after oral administration and produced plasma concentrations in the presumed therapeutic range and dose proportional increases in exposures with doses ranging from 25 to 150 mg. Clearance was rapid, with a mean half-life ( $t_{1/2}$ ) of 2 to 4 hours. Consumption of a high fat meal had a modest effect on COR388 HCl exposure, which is not likely to be of clinical relevance. Single doses of COR388 HCl ranging from 5 to 250 mg were safe and well tolerated when administered to healthy volunteers, although there was only 1 subject in the 250 mg dose cohort. Treatment-emergent adverse events (TEAEs) were infrequent, mostly mild in severity, and transient. There were no deaths, Serious Adverse Events (SAEs), or TEAEs leading to study drug discontinuation during the study. There were no clinically meaningful changes in safety laboratory findings, electrocardiograms (ECGs), vital signs, or physical examinations observed during the study.

The multiple ascending dose study revealed that oral doses of COR388 HCl ranging from 25 to 100 mg every 12 hours were safe and well tolerated when administered to normal healthy volunteers 55 to 70 years of age and Alzheimer's disease (AD) subjects 58 to 83 years of age. Subjects who received COR388 HCl experienced infrequent TEAEs, which were mostly mild in severity and transient. There were no deaths, SAEs, or TEAEs leading to study drug discontinuation during the study. There were no clinically meaningful changes in laboratory parameters, vital signs, ECGs, or physical examination findings observed during the study. COR388 HCl was readily bioavailable after oral administration, with good tissue distribution and

rapid clearance. The results of the Phase 1a/b trials are described in more detail in the IB.

Safety and PK data from the Phase 1 a/b program along with appropriate preclinical chronic toxicology and other studies enabled Cortexyme to select appropriate doses and move forward with the Phase 2/3 program.

### 3 STUDY OBJECTIVES

The objectives of the study are to:

- Assess the efficacy of 2 dose levels of COR388 HCl in Alzheimer's disease (AD) subjects; and
- Assess the safety and tolerability of 2 dose levels of COR388 HCl in AD subjects.

### 4 INVESTIGATIONAL PLAN

#### 4.1 Overall Study Design and Plan

This is a randomized, double-blind, placebo-controlled study that will assess the efficacy, safety, and tolerability of 2 dose levels of COR388 HCl in subjects with probable AD dementia according to the National Institute on Aging-Alzheimer's Association (NIA-AA) criteria (McKhann 2011). The study will enroll approximately 573 generally healthy male and female subjects,  $\geq 55$  and  $\leq 80$  years of age. Enrolled subjects must have a documented diagnosis of probable AD dementia with clinical evidence of progressive cognitive decline in the last year. Clinical decline will be defined as the evidence of progressive cognitive decline on subsequent evaluations based on information from informants and/or cognitive testing in the context of either formal neuropsychological evaluation or standardized mental status examinations for probable AD dementia (McKhann 2011). The subject should not have other conditions or brain imaging abnormality that can explain the symptoms of dementia. A Lumbar Puncture (LP) will be performed at baseline (Visit 2) and at end of treatment period week 48 (Visit 10) or early termination visit (ET). Cerebrospinal fluid (CSF) will be tested for measurement of bacterial DNA (*Pg*) using quantitative polymerase chain reaction (qPCR), biomarkers of AD, and gingipain activity. Saliva, and blood will be analyzed for measurements of biomarkers of AD and neuroinflammation, and for the presence of bacterial deoxyribonucleic acid (DNA) of *Porphyromonas gingivalis* (*P. gingivalis* [*Pg*]) using qPCR.

A subset of sites will be selected to monitor subjects for clinical evidence of periodontitis in addition to AD. An oral examination will be conducted by a study dentist/hygienist at these sites to assess for the presence of clinical evidence of periodontitis. Subjects will have follow-up oral examinations at 24 and 48 weeks. Subgingival plaque (SGP) and buccal cell swabs will be collected in addition to saliva at these sites and analyzed for measurements of biomarkers associated with *P. gingivalis* DNA, proteins, and inflammation.

Due to the nature of AD, subjects must identify a primary caregiver prior to enrollment in the study who will assist the subject with study participation. The primary caregiver must sign a caregiver informed consent.

The safety of study participants will be evaluated throughout the study by repeated physical examinations, vital signs, safety laboratory tests, 12-lead electrocardiograms (ECGs), Columbia-Suicide Severity Rating Scale (C-SSRS), magnetic resonance imaging (MRI), and assessments of treatment-emergent adverse events (TEAEs). Periodic safety reviews will be conducted during the study.

The study will consist of 3 periods: a screening period of up to 6 weeks, a treatment period of up to 48 weeks, and a safety follow-up period of 6 weeks. An interim analysis may be conducted to reassess the sample size and evaluate for efficacy after 24 weeks of treatment on key outcome measures.

During the screening period, the eligibility of subjects will be confirmed according to the Schedule of Evaluations ([Table 1](#)).

Eligible subjects will be randomized 1:1:1 to receive one of the following treatments:

- 80 mg COR388 HCl, twice daily (bid);
- 40 mg COR388 HCl, bid; or
- Placebo, bid.

The study drug will be provided in capsule form for oral administration. All capsules will be identical in appearance.

#### **4.1.1 Scientific Rationale for Study Design**

The primary objective of the study is to assess the efficacy of COR388 HCl in the treatment of AD. Based on the postulated mechanism of action of this compound, treatment is expected to slow or prevent further neurodegeneration, cognitive decline, and accumulation of pathology in AD subjects should COR388 HCl be effective. Available data indicate that Alzheimer's Disease Assessment Scale-Cognitive Subscale 11 (ADAS-Cog 11) score increases by 2-4 points per year on average in subjects with mild to moderate AD ([Ito 2013](#), [Wattmo 2016](#)). Therefore, a treatment period of 48 weeks was selected to allow sufficient time to demonstrate at least 2.5 points difference between active treatment and placebo on ADAS-Cog 11 at the end of treatment period. The doses of 40 and 80 mg were selected to provide plasma levels of COR388 above the levels found to be therapeutic in animal models, while maintaining safe exposure levels based on preclinical and clinical data available to date. The objective of the open label extension portion of the study is to evaluate the safety and efficacy of COR388 HCl treatment in all subjects who want to participate and meet eligibility criteria.

The frequency of visits is selected to provide close monitoring of subjects' safety, without putting undue burden on the subjects and their caregivers. Similarly, study assessments are selected to provide the essential data needed to assess the

efficacy and safety of COR388 HCl, without burdening study subjects with unnecessary procedures or lengthy site visits.

#### **4.1.2 Efficacy Evaluations**

##### Primary Endpoint

The two co-primary endpoints are:

- Mean change in Alzheimer's Disease Assessment Scale-Cognitive Subscale 11 (ADAS-Cog 11) from baseline to the end of treatment period; and
- Mean change in Alzheimer's Disease Cooperative Study Group-Activities of Daily Living (ADCS-ADL) from baseline to the end of treatment period.

##### Secondary Endpoints

Secondary endpoints in all subjects include:

- Change in Clinical Dementia Rating-Sum of Boxes (CDR-SB);
- Change in Mini-Mental State Examination (MMSE); and
- Change in Neuropsychiatric Inventory (NPI).

##### Exploratory Endpoints

Exploratory endpoints in all participating subjects include change from screening/baseline and/or Visit 2 to the end of treatment period in the following measures:

- Blood-based biomarkers in serum and peripheral blood mononuclear cells (PBMCs); and
- Saliva biomarkers of *P. gingivalis* infection and inflammation.
- Cerebrospinal fluid:
  - CSF A $\beta$ 42, total Tau, and phosphorylated Tau;
  - Bacterial DNA in the CSF on quantitative polymerase chain reaction (qPCR); and
  - CSF biomarkers.

Exploratory endpoints in subjects participating in sub-studies include change from screening/baseline to the end of treatment period in the following measures:

- Winterlight Speech Assessment (only in English speaking subjects (primary language and only in the US and UK);
- Magnetic resonance imaging sub-study (subjects who have MRIs done in conjunction with the study):
  - Hippocampal volume; and
  - Cortical thickness.

- Clinical periodontitis sub-study (subjects enrolled at selected sites):
  - Pocket Depth (PD);
  - Clinical Attachment Level (CAL) at 6 sites per tooth (distobuccal [DB], buccal [B], mesiobuccal [MB], distolingual [DL], lingual [L], and mesiolingual [ML]);
  - The percentage of sites with Bleeding on Probing (BOP); and
  - Biomarkers of *P. gingivalis* infection and inflammation in subgingival plaque (SGP) and buccal cell swabs.

### Safety Endpoints

Safety endpoints include:

- The incidence and severity of TEAEs;
- Vital signs and physical examinations;
- Laboratory values;
- MRI scans;
- 12-lead ECGs; and
- C-SSRS.

### **4.1.3 End of Study Definition**

End of study is Safety Follow-up Visit 11 or Visit OLE-9 (if subject participates in the open label extension portion of the study), unless the Investigator determines that treatment of a given subject should be stopped or interrupted for safety or tolerability reasons, the subject withdraws consent, or the Sponsor decides to stop the study.

## **5 STUDY DRUG ADMINISTRATION AND MANAGEMENT**

### **5.1 Dose Preparation and Administration**

Each subject will receive study treatment according to the randomization scheme. The study drug will be provided in capsule form for oral administration. Subjects will be instructed to take the capsules with water twice a day, one capsule after waking in the morning and one before bed, ideally 12 hours apart and no less than 6 hours apart.

### **5.2 Randomization to Treatment Groups**

Subjects who meet all eligibility criteria will enter the treatment period and will be randomized 1:1:1 to receive 40 mg COR388 HCl, 80 mg COR388 HCl, or placebo twice a day. Randomization will be stratified by baseline MMSE (MMSE  $\geq 12$  and  $\leq 18$ , and MMSE  $\geq 19$  and  $\leq 24$ ) and Apolipoprotein E (ApoE4 positive either homozygous or heterozygous vs. all others) genotype to assure balanced distribution of mild and moderate AD and a balanced distribution of ApoE4 subjects, across treatment arms. All participants will be centrally assigned to randomized

study intervention using an Interactive Response System (IRS). All subjects in the open label extension portion of the study will receive 40 mg or 80 mg COR388 HCl.

### **5.3 Packaging and Labeling**

Study drug will be packaged in blister packs and assembled into weekly cards each containing 16 capsules: 2 capsules for each day of the week and 2 additional capsules to be used only if instructed by the Investigator (late visits, damaged or lost capsules, etc.). The capsules will be identical in appearance, but their contents will depend on the subject's treatment assignment. The cards containing the blister packed capsules will be labeled in compliance with country-specific labeling requirements.

### **5.4 Study Drug Supply, Storage, and Handling**

#### **5.4.1 COR388 HCl**

The COR388 HCl capsules are orange, opaque, size 3 hydroxypropyl methylcellulose (HPMC) capsules containing the appropriate dose of COR388 HCl based on the treatment arm. The capsules should be stored at room temperature.

The study drug will be kept in a secure location that is accessible only to study personnel whom the Investigator has authorized to dispense/prepare study drug.

#### **5.4.2 Placebo**

The placebo capsules are orange, opaque, size 3 HPMC capsules containing microcrystalline cellulose. Placebo capsules must be stored at room temperature.

The placebo capsules will be kept in a secure location that is accessible only to study personnel whom the Investigator has authorized to dispense/prepare study drug.

#### **5.4.3 Unblinding of Individual Study Subjects**

From Screening (Visit 1) through the Safety Follow-up Visit (Visit 11), the Investigator should not become unblinded unless knowledge of the treatment is required for the subject's safety and medical care.

In the event of an SAE requiring identification of the study drug administered to an individual subject, the Investigator will access the IRS using the emergency unblinding instructions. The IRS will record the name of the Investigator making the request, the date and time of the request, and the subject number and age. The Sponsor will be informed within 24 hours if unblinding occurs.

The Investigator will attempt to consult with the Medical Monitor regarding the need to unblind the treatment assignment for the subject, if time allows. At all times, the safety and well-being of any subject outweighs the need to consult with the Medical Monitor. In any event, the Investigator will contact the Medical Monitor and

Cortexyme within 24 hours of breaking the blind. The Investigator will be responsible for documenting the time, date, and reason for the unblinding and the names of the personnel involved. Every effort should be made to avoid unblinding other study personnel.

## **5.5 Drug Inventory and Accountability**

The Investigator must keep an accurate accounting of the number of investigational product units delivered to the site, dispensed to subjects, returned to the Investigator by the subject, and returned to the Sponsor or other disposition during and at the completion of the study. The investigational product must be dispensed to subjects only by an appropriately qualified person. The investigational product is to be used in accordance with the protocol by subjects who are under the direct supervision of the Investigator. Investigators should maintain records that document adequately that the subjects were provided the doses specified by the protocol and reconcile all investigational products received at the site before final disposition. At the end of the study, or as directed, all study drugs, including unused, partially used, and empty containers, will be returned to the Sponsor/designee or will be destroyed.

## **5.6 Treatment Compliance**

Investigational product containers must be returned at each visit, as compliance will be assessed by capsule counts. Noncompliance is defined as taking less than 80% or more than 120% of investigational product during any outpatient evaluation period (visit to visit). Discontinuation for noncompliance is at the Investigator's discretion and is to be noted on the electronic Case Report Form (eCRF).

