***Safety Follow-up Period***

After completion of study treatment, subjects will continue to be monitored on the study for 6 weeks and will have a phone call to assess safety at Weeks 49 and 51 and will return for the Safety Follow-up Visit (Week 54).

For subjects with early termination, end of study procedures (Week 48) will be performed, and subjects will be encouraged to return to the clinic for the Safety Follow-up Visit after 6 weeks. Phone calls will be performed to assess safety at Week 1 and Week 3 after end of study procedures are performed.

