### **11.3 Final Analysis**

#### **11.3.1 Analysis Populations**

- **Intent-To-Treat Population (ITT):** The ITT population will include all subjects who are randomized regardless of whether or not they took study drug. This population will serve as the basis for all efficacy analyses. When change from baseline is assessed, subjects will be included in the analysis only if both a baseline and a postbaseline measure are available.
- **The Per Protocol population (PP):** The PP population will include all ITT subjects who do not have any major protocol deviations that would affect efficacy (e.g., <80% treatment compliance, taking a prohibited medication). Major protocol deviations will be reviewed and determined prior to unblinding. The PP population will be used for supportive sensitivity analyses.
- **Safety Population:** The Safety population will include all subjects who receive at least one dose of study drug. Safety analyses will be performed using the Safety population, and subjects will be analyzed according to the treatment they actually receive.

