### **12.13 Removal of Subjects from Therapy or Assessment**

Liver Safety Monitoring (laboratory analyte testing) must be performed at each study visit within the prespecified visit window (see [Table 1](#) and [Table 2](#), Schedule of Evaluations) OR the study drug dosing must be temporarily halted until the testing is done.

Subjects who discontinue IP dosing for IP-related safety reasons will not be permitted to resume IP treatment and must be followed until the safety concern (e.g. transaminase elevations) or an existing AE has stabilized or resolved/returned to baseline. At that time subject's participation in the study must be terminated early and V10/ET procedures must be performed. Subjects should remain in the study through final 6-weeks safety follow up period which ends with a final study visit.

A subject will be considered to have completed the study when he or she completes Visit 11. If a subject is discontinued at any time after randomization into the study, the Investigator will make every effort to follow the subject and complete the Visit 10/Early Termination assessments.

A termination electronic case report form (eCRF) page should be completed for every subject who receives investigational product, whether or not the subject completes the study. The reason for any early discontinuation should be indicated on this form. The primary reason for a subject discontinuing early should be selected from the following standard categories of early termination:

- *Adverse Event (Adverse Reaction)*: Clinical or laboratory events occurred that, in the medical judgment of the Investigator for the best interest of the subject, are grounds for discontinuation. This includes serious and nonserious adverse events (AEs) regardless of relation to the investigational product.
- *Death*: The subject died.
- *Withdrawal of Consent*: The subject desired to withdraw from further participation in the study in the absence of an Investigator-determined medical need to withdraw. If the subject gave a reason for withdrawing, it should be recorded in the eCRF.

- *Protocol Violation*: The subject's findings or conduct failed to meet the protocol entry criteria or failed to adhere to the protocol requirements (e.g., drug noncompliance, failure to return for defined number of visits). The violation necessitated early discontinuation from the study.
- *Lost to Follow-Up*: The subject stopped coming for visits and study personnel were unable to contact the subject.

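### Discontinuation for noncompliance is not separated from leaving the study, so subjects stopped early have no Week 40 and 48 co-primary scores although efficacy is analysed in all randomized subjects

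*Protocol*

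**What the plan says.** Section 5.6 sets the threshold: "Noncompliance is defined as taking less than 80% or more than 120% of investigational product during any outpatient evaluation period (visit to visit"). It then leaves the consequence open: "Discontinuation for noncompliance is at the Investigator's discretion and is to be noted on the electronic Case Report Form (eCRF"). Nothing in 5.6 says whether this means stopping capsules or ending participation.

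Section 12.13 lists the reasons to be entered on the termination form. One of them, Protocol Violation, covers a subject who "failed to adhere to the protocol requirements (e.g., drug noncompliance, failure to return for defined number of visits"), and closes with "The violation necessitated early discontinuation from the study".

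For anyone discontinued after randomization, 12.13 says that "the Investigator will make every effort to follow the subject and complete the Visit 10/Early Termination assessments". The synopsis, under Safety Follow-up Period, adds: "For subjects with early termination, end of study procedures (Week 48) will be performed". It also provides for phone calls one and three weeks later and encourages a clinic visit after six weeks. Section 7.12 shows that this last visit repeats ADAS-Cog 11 and ADCS-ADL.

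Section 11.3.1 states: "The ITT population will include all subjects who are randomized regardless of whether or not they took study drug". It makes this set the basis of all efficacy analyses and gives compliance below 80% as an example of a deviation that removes a subject from the Per Protocol set. Section 11.3.2.1 defines both co-primary endpoints as the average of Weeks 40 and 48, analysed by MMRM.

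**The concern.** The analysis set is defined without regard to drug intake, yet poor drug intake can end the collection of the scores to be analysed. A subject stopped at, say, Week 14 contributes the Week 12 visit, an early-termination score and perhaps one score six weeks later. None of these is a Week 40 or 48 outcome, and no analysis plan can restore scores that were never collected.

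The missing-at-random MMRM then predicts the later course from the subject's own earlier scores and from others in the same arm who mostly stayed on drug. If noncompliance follows decline or side effects, that prediction may be too favourable for an active arm, and the estimate moves toward the effect in those who kept taking drug.

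The threshold is easily crossed. From Visit 2 to Visit 3 is 14 days at two capsules a day, or 28 capsules. Missing 6 gives 22/28 = 78.6%, so three days of missed doses in that interval make discontinuation possible.

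**Working it through.** **1. The passages side by side**

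- Section 5.6: noncompliance in any one visit interval may lead to discontinuation, at discretion, with drug or study not specified.
- Section 12.13: drug noncompliance is an example of a reason for discontinuation from the study.
- Section 12.13, Section 7.12 and the synopsis: after discontinuation come Visit 10/ET, two phone calls and an encouraged visit at six weeks. No text keeps the subject on the Week 12, 24, 40 and 48 efficacy schedule.
- Sections 11.3.1 and 11.3.2.1: all randomized subjects, whether or not they took drug, with the outcome at Weeks 40 and 48.

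For a subject stopped well before Week 40, the first three items leave the outcome in the fourth unmeasured.

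**2. The plan's own power figure (Section 11.2)**

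Inputs: 191 randomized per arm, 10% dropout, ADAS-Cog 11 difference 2.5, SD 7.1, two-sided alpha 0.05.

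- Evaluable: 191 × 0.90 = 171.9, or 172 per arm.
- Power = Φ(δ / (SD × √(2/n)) − 1.96) = Φ(2.5 / (7.1 × √(2/172)) − 1.96) = Φ(3.265 − 1.96) = 0.904.

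The stated value of about 90% reproduces.

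**3. Power if removals come on top of the planned dropout**

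The protocol gives no removal rate, so f = 2%, 5% and 10% are assumptions. Evaluable n = 191 × (1 − 0.10 − f). The last column uses the ADCS-ADL inputs of Section 11.2 (3.9 points, SD 10.5).

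| f | n per arm | ADAS-Cog 11 power | ADCS-ADL power |
|---|---|---|---|
| 0 | 172 | 90.4% | 93.1% |
| 2% | 168 | 89.8% | 92.6% |
| 5% | 162 | 88.7% | 91.7% |
| 10% | 153 | 86.8% | 90.1% |

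At 5%: 191 × 0.85 = 162.35, and Φ(2.5 / (7.1 × √(2/162.35)) − 1.96) = Φ(3.172 − 1.96) = 0.887. Section 11.2 states about 95% for ADCS-ADL; that difference is not part of this point.

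**4. Possible overstatement of the effect**

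Assume that a fraction f of an active arm is removed, that these subjects would have ended at the placebo level, and that the MMRM estimate stays at the on-drug 2.5 points.

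- Effect had they been followed: (1 − f) × 2.5 = 2.45, 2.375 and 2.25 for f = 2%, 5% and 10%.
- Overstatement: f × 2.5 = 0.05, 0.125 and 0.25 points.

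This is an upper value under these assumptions. Partly retained benefit, or earlier scores that already show decline, would make it smaller.

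**The case against.** The strongest reply is that 12.13 is a list of reason codes for a form. It records cases in which a violation made discontinuation necessary and does not tell anyone to remove noncompliers. That is right. The fault is an ambiguity in 5.6 that 12.13 resolves in the direction of the study. It still leaves no text that keeps such subjects under observation.

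A reader might infer that a per-protocol selection enters the primary analysis. The documents do not support this: the subjects remain in the ITT set and their earlier post-baseline scores remain in the model. What is lost is the later scores.

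A reader might also infer that these removals never have a safety reason. That does not hold either. Noncompliance in 5.6 includes intake above 120%, Section 9.4 treats overdose as a matter for close monitoring, and some entry criteria in 6.2 are safety criteria.

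The sensitivity analyses in 11.3.2.1.1 include control-based imputation, in which active-arm subjects who discontinue follow the placebo course. This addresses the bias scenario above and gives real reassurance. It rests on modelled values, however, and stands beside the primary analysis rather than in it.

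Two further points stand in part. The planned 10% dropout does not exclude this reason; if these removals fall within it, power stays at 90.4%. Removal that differs by arm is possible but not shown, and the trial is double-blind with identical capsules.

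**Conclusion.** The point holds as a gap in the retention rules. Sections 5.6 and 12.13 together allow noncompliance to end participation, and the co-primary scores at Weeks 40 and 48 are then not collected in subjects whom 11.3.1 means to analyse whatever their drug intake. No figure in the protocol is wrong on this account.

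The size cannot be known from the document, because both the noncompliance rate and the use of discretion are unstated. Under assumed removal of 2% to 10% with complete loss of benefit, the overstatement is at most about 0.05 to 0.25 ADAS-Cog 11 points against a planned 2.5. A 5% loss beyond the planned 10% costs 1.7 percentage points of power (90.4% to 88.7%). These effects are modest. The case for change rests on avoidable and possibly informative missing data that is cheap to prevent.

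**What to change.** In 5.6 and 12.13, distinguish stopping study drug from leaving the study. State that noncompliance or another protocol deviation does not by itself end study participation, and that subjects who still consent keep the scheduled efficacy visits through Weeks 40 and 48. Handle noncompliance analytically through the Per Protocol set, which 11.3.1 already provides.

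Who stops study drug is left as it is. The termination reason codes need not be deleted: removing a code keeps nobody in the study, since the same subject could be recorded as Other.

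The cost is protocol wording and some already planned visits for subjects off drug, with no new procedure. The effect estimate may be slightly smaller, because it will include outcomes of subjects who stopped taking drug.
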